	
Secondary Efficacy Endpoints
 
 • Proportion of women in the relugolix Group B versus the placebo Group C who achieve a menstrual blood loss volume of < 80 mL AND at least a 50% reduction from baseline menstrual blood loss volume over the last 35 days of treatment, as measured by the alkaline hematin method. 
The following secondary endpoints will be assessed comparing each relugolix treatment group to placebo inferentially and relugolix Group A to Group B descriptively:
 
 • Time to achieving a menstrual blood loss volume of < 80 mL AND at least a 50% reduction from baseline menstrual blood loss volume as measured by the alkaline hematin method; • Change from Baseline to Week 24 in menstrual blood loss; • Proportion of women who achieve amenorrhea over the last 35 days of treatment as measured by the alkaline hematin method; • Time to amenorrhea as measured by the alkaline hematin method; • Proportion of women with a hemoglobin below the lower limit of normal at Baseline who achieve an increase of ≥ 1 g/dL from Baseline at Week 24; • Change from Baseline to Week 24 in the Menorrhagia Impact Questionnaire Score for physical activities; • Change from Baseline to Week 24 in the Menorrhagia Impact Questionnaire Score for social and leisure activities; • Proportion of women who achieve a mean Numerical Rating Scale score for uterine fibroid-associated pain over the last 35 days of treatment that is at least a 30% reduction from Baseline in the subset of women with a maximum pain score ≥ 4 during the 35 days prior to randomization; • Change from Baseline to Week 24 in uterine volume; and • Change from Baseline to Week 24 in uterine fibroid volume. 
Safety Endpoints
 
 • Treatment-emergent adverse events, change in vital signs (including weight), clinical laboratory tests, and electrocardiograms; • Percent change from Baseline to Weeks 12 and 24 in bone mineral density at the spine (average of L1-L4), total hip, and femoral neck as assessed by DXA; • Incidence of vasomotor symptoms. 
Pharmacokinetic and Pharmacodynamic Endpoints
 
 • Pre-dose trough concentrations (C_t) of relugolix, estradiol, and norethindrone from Baseline through Week 24; • Changes from Baseline to Week 24 in pre-dose concentrations of LH, FSH, estradiol, and progesterone.
--	--

	
Exploratory Endpoints
 
 • Change from Baseline to Week 24 in the Uterine Fibroid Scale – Quality of Life Symptom Severity and Health-related Quality of Life subscales comparing each relugolix treatment group to placebo inferentially and the two relugolix groups descriptively; • Change from Baseline to Week 24 in the European Quality of Life Five-Dimension Five-Level scale comparing each relugolix treatment group to placebo inferentially and the two relugolix groups descriptively.
Statistical Methods	
Efficacy	

The efficacy analyses will be conducted using an Intent-to-Treat (ITT) Population defined as all randomized patients, unless otherwise specified in the statistical analysis plan. Randomization will be 1:1:1 with the stratification variables of geographic region and mean screening menstrual blood loss volume (mL per alkaline hematin method) as follows:
	

 • Geographic Region: North America versus Rest of World; • Mean screening menstrual blood loss volume: < 225 mL versus \geq 225 mL. 	

The randomization stratification factors will be incorporated into inferential testing of all efficacy endpoints, unless otherwise specified.
	

The primary hypothesis tested in this study is whether relugolix co-administered with 1.0 mg estradiol and 0.5 mg norethindrone acetate is superior to placebo in the percentage of women who achieve both a menstrual blood loss volume of < 80 mL AND at least a 50% reduction in menstrual blood loss volume over the last 35 days on treatment as compared with Baseline.
	

The point estimate and 2-sided 95% confidence interval of the difference in the proportion will be calculated between the relugolix Group A and placebo Group C. The between-treatment comparisons will be performed using the Cochran-Mantel-Haenszel method.
	

The comparisons of the relugolix arms versus placebo will be performed for the secondary efficacy and safety endpoints using appropriate statistical methods. Comparisons between the two relugolix arms will be descriptive. A closed testing procedure will be used to control the overall type I error rate of 5% across primary and secondary endpoint testing. Details of this procedure will be provided in the statistical analysis plan.
	
Sample Size	

Assuming a placebo control response rate of 25%, the assessment of the superiority of relugolix 40 mg co-administered with low-dose hormonal add-back therapy (Group A) versus placebo (Group C) in the proportion of patients who achieve both a menstrual blood loss volume of < 80 mL AND at least a 50% reduction in menstrual blood loss volume over the last 35 days of treatment, a sample size of 260 (130 patients in each of the relugolix and placebo arms) will provide > 99% power to detect a difference of greater than 30 percentage points using a 2-sided test at significance level of 0.05. The total sample size for the study will be approximately 390 patients (130 patients in each of the 3 arms).
	
Safety	

Safety assessments will include treatment-emergent adverse events, vital signs, physical examinations, clinical laboratory tests, 12-lead electrocardiograms, endometrial biopsies, and assessments of bone mineral density. Safety analyses will be based on all randomized patients who receive any amount of study drug (safety population). Drug exposure will be summarized by descriptive statistics. Severity of all treatment-emergent adverse events will be evaluated by the investigator based on the National Cancer Institute's Common Terminology Criteria for Adverse Events (CTCAE), version 5.0 and will be coded to preferred term, higher level term, and system organ class using the Medical Dictionary for Regulatory Activities (MedDRA). The number and percentage of patients with adverse events will be
	

presented by MedDRA system organ class and preferred term, relationship to study drug, and severity. Descriptive statistics will be used rather than inferential statistics. Laboratory values also will be classified by toxicity grade based on the National Cancer Institute's CTCAE, version 5.0. Laboratory shift tables of the Baseline results to each of the subsequent visits will be produced. Bone mineral density will be evaluated in all patients at the lumbar spine (L1-L4), total hip, and femoral neck at the Baseline, Week 12, and Week 24 visits and the absolute, percent, and standardized changes from baseline will be summarized. Vasomotor adverse events will be separately summarized.

A chartered independent Data and Safety Monitoring Board will monitor all available safety data, including bone density assessments, on an ongoing basis during this study.

Pharmacokinetics and Pharmacodynamics

The PK concentration data (relugolix, estradiol, and norethindrone pre-dose) and pharmacodynamics concentration data (LH, FSH, estradiol, and progesterone pre-dose) will be listed and summarized by treatment arm and visit. In addition, the PK data from this study will be combined with PK data from other studies to define a population PK model, which will be reported separately. Exposure-response analyses of the primary efficacy endpoint and safety will be conducted to assess the effect of relugolix exposure on outcomes.

1.1. Schedule of Activities

Table 1-1 Schedule of Activities for Study MVT-601-3001

VISIT NAME	SCREENING PERIOD ^a				RANDOMIZED TREATMENT PERIOD							SAFETY FOLLOW-UP		
	Screening 1 ^b	Screening 2 ^b	Screening 3 ^c (if MBL is \geq 80 mL at 1st Screening menses)	Screening 4 ^b	Baseline Day 1 ^d (if MBL is \geq 80 mL/cycle for 2 cycles)	Week 4	Week 8	Week 12	Week 16	Week 20	Week 24 (or Early Termination of Study Drug)	Un-scheduled	Follow-up ^e (~30 days after last dose of study drug)	
Day of Study Drug Treatment					1	29	57	85	113	141	169			197
Visit Window Timing (days)	Within 4 days after completion of menses	Within 4 days after completion of Screening 1 menses	Within 10 days of Screening 2 visit	Within 4 days after completion of 2nd Screening menses	Within 4 days of the start of menses	\pm 7	\pm 10			-3 to + 10				
Informed Consent	X													
Medical History	X													
Review Eligibility Criteria	X		X	X	X									
Vital Signs	X		X		X	X	X	X	X	X	X	X	X	X
Height	X													
Weight	X				X						X	X	X	
Temperature	X				X							X	X	
Adverse Event Collection ^f	X	X	X	X	X	X	X	X	X	X	X	X	X	X
Concomitant Medications	X	X	X	X	X	X	X	X	X	X	X	X	X	X
Complete Physical Examination, Including Visual Acuity ^g	X				X						X			
Gynecologic Examination with Pap Test, if applicable			X ^h								X			

VISIT NAME	SCREENING PERIOD ^a				RANDOMIZED TREATMENT PERIOD							SAFETY FOLLOW-UP	
	Screening 1 ^b	Screening 2 ^b	Screening 3 ^c (if MBL is ≥ 80 mL at 1st Screening menses)	Screening 4 ^b	Baseline Day 1 ^d (if MBL is ≥ 80 mL/cycle for 2 cycles)	Week 4	Week 8	Week 12	Week 16	Week 20	Week 24 (or Early Termination of Study Drug)	Un-scheduled	Follow-up ^e (~30 days after last dose of study drug)
Signs and Symptoms-Directed Physical Exam			X			X	X	X	X	X		X	X
12-Lead Electrocardiogram			X		X			X			X	X	X
Clinical Laboratory Tests ^l	X	X			X ^{l, j}	X	X	X	X	X	X ^{l, k}	X ^l	X
PK Sample ^m					X	X		X			X	X ^l	
PD Sample ⁿ and Administer Dose of Study Drug in Clinic	X				X	X	X	X	X	X	X		X
PGx Sample ^o					X								
Pregnancy Test (Urine)	X		X		X	X	X	X	X	X	X		
Urinalysis	X				X								
Mammogram ^p			X										
Transvaginal or Transabdominal Ultrasound ^q			X									X	
Endometrial Biopsy ^r			X									X ^s	
Bone Densitometry ^t			X					X				X	
Randomization ^u					X								
Dispense Feminine Products	X	X			X	X	X	X	X	X			
Dispense Study Treatment					X	X	X	X	X	X			
Patient eDiary ^v			X	X	X	X	X	X	X	X	X		
Feminine Product Collection and Venous Blood Sample ^w		X		X		X	X	X	X	X	X		
MIQ					X	X	X	X	X	X	X		
UFS-QoL					X			X				X	
EQ-5D					X							X	
Treatment Compliance						X	X	X	X	X	X	X	

VISIT NAME	SCREENING PERIOD ^a				RANDOMIZED TREATMENT PERIOD							SAFETY FOLLOW-UP		
	Screening 1 ^b	Screening 2 ^b	Screening 3 ^c (if MBL is ≥ 80 mL at 1st Screening menses)	Screening 4 ^b	Baseline Day 1 ^d (if MBL is ≥ 80 mL/cycle for 2 cycles)	Week 4	Week 8	Week 12	Week 16	Week 20	Week 24 (or Early Termination of Study Drug)	Un-scheduled	Follow-up ^e (~30 days after last dose of study drug)	
Status of Menstruation Recovery														X

Notes:

Abbreviations: EQ-5D, European Quality of Life Five-Dimension Five-Level Scale; MBL, menstrual blood loss; MIQ, Menorrhagia Impact Questionnaire; Pap, Papanicolaou; PD, pharmacodynamics; PGx, pharmacogenomics; PK, pharmacokinetics; UFS-QoL, Uterine Fibroid Score – Quality of Life

- a. The screening period should be initiated after the informed consent form is signed and any required washout for excluded medications or devices is complete.
- b. Visit to occur within 4 days of the completion of menses.
- c. Visit to occur within 10 days after Screening 2 visit if the menstrual blood loss is determined to be ≥ 80 mL. The Screening 1 or Screening 2 visits for alkaline hematin menstrual blood loss may be repeated at the discretion of the investigator if one menstrual cycle does not meet MBL criteria thought to be due to inadequate collection for a highly motivated patient.
- d. The Baseline Day 1 visit should occur within 4 days of the onset of menses. Collect clinical laboratory, PK sample, pre-dose PD sample, pregnancy and urinalysis test samples prior to first dose of study drug. The patient must complete MIQ, UFS-QoL, and EQ-5D questionnaires prior to first dose of study drug.
- e. Follow-up visit: For women who do not continue into the open-label extension study (MVT-601-3003), a follow-up visit to assess safety will be scheduled approximately 30 days after the last dose of study drug, or the date of initiation of another investigational agent or hormonal therapy or surgical intervention, whichever occurs first (ie, ~Week 28 for patients who complete the study or ~4 weeks after an Early Termination visit).
- f. Collect serious adverse event information from the time of signed informed consent through approximately 30 days after the last dose of study drug, or the date of initiation of another investigational agent or hormonal therapy or surgical intervention, whichever occurs first. Collect nonserious adverse event information from the Baseline Day 1 visit through approximately 30 days after the last dose of study drug, or the date of initiation of another investigational agent or hormonal therapy or surgical intervention, whichever occurs first.
- g. Complete Physical Exam (not including a gynecological examination). Visual acuity must be assessed with a standard eye chart. The patient should wear any prescription glasses or contacts during the assessment.
- h. Papanicolaou test must be conducted for women without a test result 6 months prior to the Screening 1 visit. Re-measurement should be performed for inadequate or false-positive results.
- i. Clinical laboratory tests at each visit include clinical chemistries and a complete blood count. Samples should be obtained in the fasted state for the Baseline and Week 24 visit clinical laboratory tests.
- j. At the Baseline Day 1 visit (clinical laboratory tests in fasted state), in addition to clinical chemistries and a complete blood count, include a lipid profile, levels of parathyroid hormone, thyroid-stimulating hormone, prolactin, iron, ferritin, and hemoglobin A1c. An additional sample will be collected at this visit and stored for possible future testing for presence of hepatitis A, B, and C if required per request from medical monitor to assess etiology of liver test abnormalities.
- k. At the Week 24 visit or Early Termination visit (clinical laboratory tests in fasted state), in addition to clinical chemistries and a complete blood count, include a lipid profile, thyroid-stimulating hormone, prolactin, and hemoglobin A1c.

- l. For an Unscheduled visit, a central safety laboratory assessment or PK sample collection is performed as needed.
- m. Pharmacokinetics samples: Samples should be obtained in the fasted since study drug is administered on an empty stomach. Collect pre-dose samples for PK analysis of relugolix, estradiol (PK lab), and norethindrone. Instruct the patient not to take her study treatment at home on these visit days and to record the time of her previous dose (ie, the dose taken the day before the visit). Administer study drug after PK and pharmacodynamics sample collections are complete (with the exception of Week 24 when no dose is administered).
- n. Pharmacodynamic samples: Samples should be obtained in the fasted since study drug is administered on an empty stomach, collect pre-dose samples for analysis of luteinizing hormone, follicle-stimulating hormone, estradiol, and progesterone concentrations. Instruct the patient not to take her study treatment at home on these visit days. Administer study drug after PK and pharmacodynamic sample collections are complete (with the exception of Screening 1 visit, Week 24 and Follow Up visits when no dose is administered).
- o. Pharmacogenomics sample: a separate pharmacogenomics consent is required before this sample may be collected. If possible, the pharmacogenomic sample should be collected from consented patients at the Baseline Day 1 visit, but it may be collected at any time during the study through Week 24 (inclusive)
- p. Patients \geq 39 years of age at the time of the Baseline Day 1 visit must have a normal mammogram (Breast Imaging Reporting and Data System category 1 to 3 or equivalent) during the screening period or within 3 months prior to the screening period; if not, schedule at the Screening 3 visit.
- q. Transvaginal or transabdominal ultrasound with saline or gel contrast must be performed to confirm the presence of uterine fibroids and the absence of any other pathology that might be responsible for the increase in menstrual bleeding, such as uterine or cervical polyps. Results must be submitted to and confirmed by a central reader prior to randomization into the study. Note: Transvaginal ultrasound is the preferred procedure. A transabdominal ultrasound may also be obtained if indicated, for example, by extension of large masses outside the pelvis.
- r. Endometrial biopsy is performed at Screening after the first acceptable alkaline hematin sample collection.
- s. Endometrial biopsy is to be performed at the Week 24 visit and may be requested for central review if abnormal.
- t. Bone densitometry (L1-L4, total hip, femoral neck) will be assessed during the screening period and the central results available prior to randomization.
- u. Randomization: After a patient is screened and the investigator determines that the patient is eligible for randomization the site staff will complete the Randomization Authorization Form and send it to the sponsor (Myovant Sciences GmbH) or sponsor designee per the instructions in the Study Reference Manual. The sponsor (or designee) will approve the patient's randomization in writing. Once the site has received approval, the patient may undergo her Baseline Day 1 visit.
- v. Patient electronic diary: Patients enter diary information on a daily basis for their compliance with (study treatment starting at Baseline/Day 1), menstrual bleeding and use of feminine products for menstrual bleeding, uterine fibroid-associated pain by the Numerical Rating Scale, and use of pain medications (analgesics) starting at Screening visit 2 and compliance with study treatment starting at Baseline/Day 1 through Week 24 or early termination.
- w. Hemoglobin: a venous blood sample must be collected each time feminine products are collected to be sent to the central laboratory conducting the alkaline hematin assessment.

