4.3.2. Exclusion Criteria

1. Has transvaginal and/or transabdominal ultrasound during the screening period demonstrating pathology other than uterine fibroids that could be responsible for or contributing to the patient's heavy menstrual bleeding, such as uterine or cervical polyps, or any other clinically significant gynecological disorder determined by the investigator to require further evaluation and/or treatment;
2. Has unexplained vaginal bleeding outside of the patient's regular menstrual cycle;
3. Has undergone myomectomy, ultrasound-guided laparoscopic radiofrequency ablation, or any other surgical procedure for fibroids, uterine artery embolization, magnetic resonance-guided focused ultrasound for fibroids, as well as endometrial ablation for abnormal uterine bleeding within 6 months prior to the Screening 1 visit;
4. Has a weight that exceeds the weight limit of the DXA scanner;
5. Has a baseline bone mineral density z-score < -2.0 at spine or total hip;

6. Has a history of or currently has osteoporosis, or other metabolic bone disease, hyperparathyroidism, hyperprolactinemia, hyperthyroidism, anorexia nervosa, or low traumatic (from the standing position) or atraumatic fracture (toe, finger, skull, face and ankle fractures are allowed). A history of successfully treated hyperparathyroidism, hyperprolactinemia, or hyperthyroidism is allowed if the patient's bone mineral density is within normal limits;
7. Has a history of the use of bisphosphonates, calcitonin/calcitriol, ipriflavone, teriparatide, denosumab, or any medication other than calcium and vitamin D preparations to treat bone mineral density loss;
8. Anticipated use of systemic glucocorticoids at an oral prednisone-equivalent dose of more than 5 mg every other day during the study. Note: topical, inhaled, intranasal, otic, ophthalmic, intraarticular, or intralesional subcutaneous are permitted without restriction;
9. Gastrointestinal disorder affecting absorption or gastrointestinal motility;
10. Has any contraindication to treatment with low-dose estradiol and norethindrone acetate, including:
 - a. Known, suspected, or history of breast cancer;
 - b. Known or suspected estrogen-dependent neoplasia;
 - c. Active deep vein thrombosis or pulmonary embolism, or history of these conditions prior to the Baseline Day 1 visit;
 - d. History of or active arterial thromboembolic disease, including stroke and myocardial infarction;

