4.5. Method of Assigning Patients to Treatment Group and Patient ID Number

After a patient is screened and the investigator determines that the patient is eligible for enrollment, the site staff will complete the Randomization Authorization Form and send it to the sponsor (Myovant Sciences GmbH) or sponsor designee per the instructions in the Study Reference Manual. The sponsor (or designee) will approve the patient's enrollment in writing. Once the site has received approval, the patient may undergo her Baseline Day 1 visit. After confirming that all inclusion criteria and no exclusion criteria are met, the site will randomize the patient to treatment by using the Interactive Voice/Web Recognition Service (IVRS/IWRS) during the patient's Baseline Day 1 visit. The IWRS will assign the patient a study treatment kit number available at the site according to the randomization code. The IVRS/IWRS will also assign the Patient Identification Number.

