6.7.2.4. Clinical Laboratory Samples

All protocol-required laboratory assessments must be conducted in accordance with the Study Reference Manual and the protocol Schedule of Activities in the synopsis (see Section 1.1). Laboratory requisition forms must be completed and samples must be clearly labelled with the Patient Identification Number, protocol number, site/center number, and visit date. Details for the preparation and shipment of samples will be provided. Reference ranges for all safety parameters will be provided to the site by the central laboratory.

The samples collected for clinical laboratory tests are listed in [Table 6-1](#).

Table 6-1 Clinical Laboratory Tests

Chemistry	Hematology	Urinalysis
Potassium	White Blood Cell (WBC) Count	Qualitative
Chloride	WBC Differential	Protein
Bicarbonate	Red Blood Cell Count	Glucose
Blood Urea Nitrogen	Hemoglobin	Occult blood
Creatinine	Hematocrit	Urobilinogen
Glucose	Mean Corpuscular Volume	Bilirubin
Calcium	Platelet Count	Pregnancy test (human chorionic gonadotropin)
Phosphate		
Magnesium		
Albumin		
Total Protein		
Alkaline Phosphatase		
Lactate Dehydrogenase		
Creatine Kinase		
Liver Function Tests including:		
Bilirubin Total		
Alanine Aminotransferase		
Aspartate Aminotransferase		
Gamma-Glutamyl Transferase		
Lipid Profile including:		
Total Cholesterol		
Low Density Lipoprotein		
High Density Lipoprotein		
Triglycerides		

Specialized Hormonal Assessments: Thyroid-Stimulating Hormone Parathyroid Hormone Prolactin Luteinizing Hormone Follicle-Stimulating Hormone Estradiol Progesterone Iron (Baseline only) Ferritin ((Baseline only) Hemoglobin A1c (Baseline and Week 24 only)		
---	--	--

A separate sample will be collected at the Day 1 visit and will be banked and tested for presence of hepatitis A, B, and C (hepatitis A antibody, IgM, hepatitis B core antibody, IgM, hepatitis B surface antigen, and hepatitis C antibody) if requested by the medical monitor for evaluation of abnormal liver function tests.

The central laboratory will perform laboratory tests for chemistry, hematology, urinalysis, and plasma and serum hormone levels. Each study site will conduct urine pregnancy tests locally.

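### Parathyroid hormone, TSH and prolactin are first drawn on the day of randomization, so they cannot inform exclusions 6 and 16a, and undiagnosed or uncontrolled disease can be identified only after dosing (minor)

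*Protocol*

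**What the plan says.** The file holds two protocol texts. Only one includes a Schedule of Activities (Section 1.1, Table 1-1). It appears to be the earlier: Section 2.2.4.2 cites an interim analysis of prostate cancer study C27002 where the other text cites a final one, and the extension study lasts 24 weeks rather than 28. Section references below are to this text unless stated otherwise.

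- **Criteria.** Exclusion 6 (Section 4.3.2, in both texts) begins "Has a history of or currently has osteoporosis, or other metabolic bone disease, hyperparathyroidism, hyperprolactinemia, hyperthyroidism". Women successfully treated for one of the three endocrine disorders are readmitted if bone density is normal. Exclusion 16a removes untreated thyroid disease or a thyroid abnormal on palpation, and readmits treated, stable hypothyroidism.
- **Screening blood.** Footnote i: "Clinical laboratory tests at each visit include clinical chemistries and a complete blood count". The pharmacodynamic sample, also drawn at Screening 1, is described in footnote n: "collect pre-dose samples for analysis of luteinizing hormone, follicle-stimulating hormone, estradiol, and progesterone concentrations".
- **Baseline Day 1.** Footnote j: "in addition to clinical chemistries and a complete blood count, include a lipid profile, levels of parathyroid hormone, thyroid-stimulating hormone, prolactin", followed by iron, ferritin and hemoglobin A1c.
- **Week 24.** Footnote k asks the sites to "include a lipid profile, thyroid-stimulating hormone, prolactin, and hemoglobin A1c"; parathyroid hormone is not repeated.
- **Assay.** Section 6.7.2.4: "The central laboratory will perform laboratory tests for chemistry, hematology, urinalysis, and plasma and serum hormone levels".
- **Randomization.** Section 4.5 and footnote u place written sponsor approval before the Baseline Day 1 visit. At that visit, "After confirming that all inclusion criteria and no exclusion criteria are met, the site will randomize the patient". Section 6.3 starts dosing the same day.

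**The concern.** The conditions in exclusion 6 sit alongside osteoporosis and metabolic bone disease, and Section 2.2.4.2 names bone mineral density loss as the serious identified risk of relugolix in women. Group B takes relugolix for 12 weeks without add-back. The protocol buys the three tests that speak most directly to these conditions, but draws the blood when the eligibility decision has already been made. A woman whose disorder nobody has yet diagnosed, or whose treated disorder is no longer controlled, can therefore be dosed before her result is known. At stake are avoidable exposure and a few women with a second cause of bone loss in the safety data. The primary efficacy comparison, the sample size and the type I error rate are not affected.

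**Working it through.** No power, alpha or rate calculation applies. The check is the order of events in Table 1-1 and its footnotes, set against the criteria.

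1. **Screening 1 to 4.** Routine bloods are chemistries and a complete blood count (footnote i). The hormone sample covers LH, FSH, estradiol and progesterone (footnote n). Neither includes parathyroid hormone, TSH or prolactin.
2. **Approval.** The investigator judges the woman eligible and the sponsor or its designee approves in writing (footnote u, Section 4.5).
3. **Baseline Day 1.** Blood for the three hormones is drawn before the first dose (footnotes d and j). Randomization (Section 5.3) and the first dose (Section 6.3) take place at the same visit.
4. **Later.** The central laboratory reports. Turnaround is not stated. Because approval at step 2 precedes even the blood draw, the results cannot inform approval however fast the assay is. They could inform the site's last check at step 3 only if returned the same day, which nothing in the document provides for.

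What is available before randomization to apply exclusions 6 and 16a:

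| Tool | Where | What it detects |
|---|---|---|
| Medical history | Section 6.2, Screening 1 | Diagnosed disease |
| Physical examination including thyroid | Sections 6.2 and 6.7.2.3 | Thyroid abnormality on palpation |
| Calcium, phosphate, alkaline phosphatase | Table 6-1 chemistries | An indirect signal; exclusion 13 attaches no rule to them |
| Central bone densitometry, z-score below -2.0 | Exclusion 5, footnote t | Bone already lost, not an active cause of loss |

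Two groups can pass all four: women with undiagnosed disease, and women readmitted as successfully or adequately treated, for whom no current hormone value is scheduled before randomization.

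The protocol treats comparable items differently. Central densitometry (footnote t) and central ultrasound confirmation (footnote q) must both be in hand before randomization. No such requirement is attached to the three hormones, and no text says what follows from an abnormal result.

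**Size.** The number affected would be 390 × (prevalence of undiagnosed or uncontrolled disease among women who pass the other criteria). The documents give no value for the second factor and no cut-off that turns an abnormal result into ineligibility, so the product cannot be computed.

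**The case against.** The strongest reply is that nothing is contradicted. Exclusion 6 is framed by diagnosis and sets no hormone threshold. Laboratory exclusions are in criterion 13, which covers hemoglobin, transaminases, bilirubin and renal function only. This stands: it is a gap in screening, not an inconsistency. It does not remove the gap, because exclusion 6 covers disease that is currently present and is not limited to known disease, whereas parts of exclusions 10 and 11 do use that qualifier.

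The reply that history, thyroid examination, chemistries and the z-score narrow the gap also stands. They narrow it; they do not close it.

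Four stronger readings are tempting and the documents do not support them.

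- *Women with these disorders will enter the trial.* Those with known active disease are excluded before randomization. Only undiagnosed or uncontrolled cases can pass.
- *A single parathyroid hormone draw must have been meant for eligibility.* Iron and ferritin are also labelled baseline-only in Table 6-1 and no exclusion uses them. Section 9.4 plans to correlate bone loss with baseline characteristics, which is a possible use.
- *The affected women would visibly change the counts of large bone loss.* Taking the phase 2 fibroid study's 12-week change on relugolix 40 mg (mean -2.28%, SD 2.194, Section 2.2.4.2) and assuming normality, the expected counts among 130 women on monotherapy are:
  - at least 4% loss: z = (-4 + 2.28)/2.194 = -0.784, probability 0.217, about 28 women;
  - at least 5% loss: z = -2.72/2.194 = -1.240, probability 0.108, about 14 women;
  - at least 6% loss: z = -3.72/2.194 = -1.696, probability 0.045, about 6 women.

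  A few extra cases would be small beside 28. They would matter beside 6 only if most of them lost that much bone, and the documents offer no evidence on that.
- *Women found ineligible would be removed or lost to the analysis.* Section 4.6 removes a woman for failed entry criteria only when continuing would put her health at unacceptable risk. Leaving the Per-Protocol Population needs a major violation (Section 9.2), and her place in the ITT Population is unaffected.

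Finally, the schedule is in the apparently earlier text. The other text keeps exclusion 6, lists the three hormones in Table 6-1 without visits, and in Section 6.2.3 names mammogram and densitometry, not these hormones, as results needed before randomization. Its own schedule is not shown, so it is not known whether the timing changed.

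**Conclusion.** The visit order is established from the text: in the schedule shown, the three hormones cannot inform exclusions 6 and 16a. It follows that women with undiagnosed or biochemically uncontrolled hyperparathyroidism, hyperthyroidism or hyperprolactinemia can be randomized and identified only after dosing. How many is unknown. Randomization spreads such women evenly across arms on average, and Section 3 makes the safety comparisons descriptive, so the consequence is avoidable exposure and added noise in the bone data, not bias between arms. The conclusion assumes that central results are not returned on the day of the draw; it applies to the schedule shown and not necessarily to the later one. It is a minor point: a cheap improvement, not a defect that threatens the trial's conclusions.

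**What to change.** In Table 1-1 and footnote j, move parathyroid hormone, TSH and prolactin to the blood draw that already takes place at Screening 1 or Screening 2. Add a sentence, parallel to footnote t, requiring that the results be available and reviewed by the investigator against exclusions 6 and 16a before randomization. Because no hormone cut-off exists, the wording should make clear that this is the investigator's judgment of whether the criterion is met. Confirm that the schedule in the later protocol text does the same.

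The change needs no new visit and no new blood draw. It has two costs. The assays would also be run in women who later fail screening. The TSH and prolactin values used as baseline for the Week 24 comparison would be up to about 11 weeks older, the length of screening in this text, unless both are repeated in the Day 1 sample.
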